8.3.3. Pharmacokinetic Parameters

The PK parameters are defined as:

- C_{max} Maximum observed concentration
- t_{max} The actual sampling time to reach maximum observed concentration
- AUC Area under the concentration – time curve

All parameters will be estimated using the actual sampling times by non-compartmental analysis methods.

8.3.4. Immunogenicity Assessments

Anti-daratumumab antibodies will be evaluated in serum samples collected from all subjects according to the [T&E Schedule](#). Daratumumab serum concentration will also be determined from all immunogenicity samples to ensure proper interpretation of the immunogenicity results.

Serum samples will be screened for antibodies binding to daratumumab and the titer of confirmed positive samples will be reported. Other immunogenicity analyses (eg, assessment of neutralizing capabilities) may be performed to further characterize the immune responses that are generated.

When both serum concentration and immunogenicity analyses are specified, they are performed on aliquots from the same blood draw and no additional sampling is required. Procedures for sample collection, preparation, identification, storage, and shipment will be provided in the Laboratory Manual or equivalent document.

A blood sample should be drawn, if possible, for determination of antibodies to daratumumab any time an infusion reaction is observed or reported during the study. Daratumumab serum concentration will also be determined from the same infusion reaction sample for the purpose of interpreting immunogenicity data. These samples will be stored and evaluated if deemed necessary. If the infusion reaction results in treatment discontinuation, then subjects should undergo all scheduled safety and efficacy evaluations. Samples collected for the analysis of daratumumab immunogenicity/serum concentration may additionally be used to evaluate safety or efficacy aspects that address concerns arising during or after the study period or for the evaluation of relevant biomarkers by the sponsor or sponsor's designee.

8.4. Pharmacokinetic/Pharmacodynamic Evaluations

If sufficient data are available, then other PK/pharmacodynamic modeling may be performed, including exploring the relationship between serum concentrations of daratumumab and endpoints of clinical efficacy and safety. Disease-related or mechanism-based biomarkers will be also explored, such as plasma EBV-DNA, blood NK cell counts, and tissue CD38 expression. If these analyses are performed, then the details and results will be presented in a separate report.

8.5. Biomarkers

Biomarker analyses are dependent upon the availability of appropriate biomarker assays and may be deferred or not performed if, during or at the end of the study, it becomes clear that the analysis will have no scientific value, or if there are not enough samples or not enough responders to allow for adequate biomarker evaluation. In the event the study is terminated early or shows poor clinical efficacy, completion of biomarker assessments is based on justification and intended utility of the data. Samples for biomarker evaluations will be collected as specified in the [T&E Schedule](#).

Circulating plasma EBV-DNA quantification

Circulating plasma EBV-DNA quantification will be monitored monthly as a biomarker of tumor load at the central laboratory. Circulating plasma EBV-DNA quantification will also be monitored at EoT visit.

Determination of CD38 and CIPs Expression

Before enrollment to the study, subjects will be required to provide tumor samples for assessment of CD38 expression based on central testing using investigational IHC methodology

under development (Section 8.1.2). Fresh biopsy samples are preferred, and if not available, archived FFPE blocks/slides are acceptable. Fresh tumor samples should be from core needle biopsy but not fine needle aspirates and should be done within 21 days of Cycle 1 Day 1; archived sample (slides or tumor block) can be acquired more than 21 days prior to Cycle 1 Day 1. If archived samples are provided instead of fresh biopsy, additional information should be provided, including but not limited to date of biopsy/resection, site/organ of biopsy, collection method, pathology report and diagnostic, treatment received after biopsy. If possible, it is also recommended to provide the following information: type of fixative used, time of execution to fix, fixation time. If FFPE sections are provided instead of block, date of section should be provided.

In addition to evaluating CD38 expression, fresh or archived biopsy samples may be evaluated in all subjects to identify markers predictive of response to daratumumab or prognostic markers for disease progression. Paraffin-embedded, formalin-fixed tumor tissue may also be subjected to DNA (eg, somatic mutations) and RNA analysis (eg, GEP, qRT-PCR, or RNA-seq) to determine if specific mutations or transcriptomic profiles (translocations, deletions, inversions, genes involved CD38 signaling pathways, or others) are associated with daratumumab response. Comparison of CD38 IHC results may be made to transcriptomic data. In addition to CD38, CIPs expression might be measured by IHC or immunofluorescent staining in a designated laboratory as an exploratory biomarker whenever samples are available. CD59, CD55 and CD46 are complement inhibitory proteins and can contribute to resistance to CDC, which may be important for daratumumab response.

If re-biopsy is needed for any clinical reasons, such as to confirm diagnosis or study pathology of new lesion, it is encouraged that FFPE slides/block to be submitted to determine CD38 and CIP expression. Correlation of biomarker expression and treatment response in the site will be studied, and the change of biomarker expression at new sites compared to the original site will also be analyzed. The information will be used to advance the understanding of daratumumab response and resistance mechanism in NKTCL patients.

Immunophenotyping.

Previous daratumumab clinical studies in MM have demonstrated that baseline immune profiles of subjects may be predictive of response to daratumumab, and that specific immune subpopulations increase (CD8+ T cells) or decrease (NK cells) with daratumumab treatment. Therefore, whole blood samples will be utilized for immunophenotyping, (performed by flow cytometry and mass cytometry/time-of-flight mass spectrometry [CyTOF]) which includes analysis of NK, T cells, and B cells as well as other potential immune cell subpopulations. NK cells are known to express CD38, and early clinical data indicates rapid decreases in absolute counts of circulating NK cells upon daratumumab dosing. It is not known how critical NK cells are for the clinical efficacy of daratumumab but based on the rapid and sustained decreased absolute counts observed across all subjects, NK cells (CD45+CD3-CD16+CD56+) can be used as a pharmacodynamic biomarker for daratumumab. In addition, preliminary data from clinical studies in MM indicate that the immune fitness of subjects at baseline may preclude response to daratumumab.

To investigate whether an immune fitness signature can be developed utilizing either flow cytometry or genomic profiling, whole blood samples may also be subject to DNA sequencing, RNA profiling or methylation assessment to identify potential predictive marker for daratumumab response and genomic alterations related to NKTCL disease mechanism, to evaluate novel technologies for immune profiling in whole blood, and to compare these methodologies to standard flow cytometry.

Since CDC is one of the key mechanisms of action for daratumumab, and normal function of complement system in the body is required for CDC activity, plasma samples will be analyzed for complement proteins, to study whether specific complement protein level is associated with daratumumab response.

Additional Collections

If it is determined at any time before study completion that additional material is needed from a formalin-fixed, paraffin-embedded (FFPE) tumor sample for the successful completion of the protocol-specified analyses, the sponsor may request that additional material be retrieved from existing samples. Also, based on emerging scientific evidence, the sponsor may request additional material from previously collected tumor samples during or after study completion for a retrospective analysis. In this case, such analyses would be specific to research related to the study drug(s) or diseases being investigated.

8.6. Safety Evaluations

Safety will be measured by AEs, laboratory test results, ECGs, vital signs measurements, physical examination findings, and assessment of ECOG performance status score. All toxicities will be graded according to the NCI-CTCAE version 4.03. Any clinically relevant changes occurring during the study must be recorded on the AE section of the eCRF. Any clinically significant abnormalities persisting at the end of the study/early withdrawal will be followed by the investigator until resolution or until a clinically stable condition is reached.

Based on the previous human experience with daratumumab, in vitro studies, and animal toxicological findings, IRRs/allergic reactions, infection, hemolysis, and thrombocytopenia will be closely monitored. As a biologic agent, immunogenicity also will be monitored. Any of the safety monitoring assessments may be performed more frequently, and AEs should be evaluated by the investigator according to the standard practice, if clinically indicated.

Any clinically relevant changes occurring during the study must be recorded on the AE section of the eCRF. Any clinically significant abnormalities persisting at the end of the study/early withdrawal will be followed by the investigator until resolution or until a clinically stable endpoint is reached. Safety assessments will be based on medical review of AE reports and the results of vital sign measurements, electrocardiograms (ECGs), physical examinations, clinical laboratory tests, ECOG performance status, and other safety evaluations at specified time points as described in the [T&E Schedule](#).

Adverse Events

Adverse events (AEs; with the exception of progression of NKTCL) will be reported by the subject (or, when appropriate, by a caregiver or surrogate) for the duration of the study. Adverse events (AEs) will be followed by the investigator as specified in Section 11, AE Reporting.

Clinical Laboratory Tests

Blood samples for serum hematology and chemistry will be collected. The investigator must review the laboratory results, document this review, and record any clinically relevant changes occurring during the study in the AE section of the eCRF. The laboratory reports must be filed with the source documents.

The following tests will be performed by the local laboratory unless otherwise noted:

- Hematology Panel

-hemoglobin	-platelet count
-white blood cell (WBC) count	-Absolute neutrophil count (ANC) and Lymphocytes
- Serum Chemistry Panel

-sodium	-aspartate aminotransferase (AST)
-potassium	-alanine aminotransferase (ALT)
-calcium	-lactic acid dehydrogenase (LDH)
-creatinine	-total bilirubin
	-direct bilirubin (for subjects with congenital bilirubinemia, such as Gilbert syndrome)
-blood glucose (fasting)	-alkaline phosphatase
- Serum or Urine Pregnancy Testing (for women of childbearing potential only and as clinically indicated)
- Hepatitis B Screening (local laboratory)

-HBsAg	-Anti-HBc
-Anti-HBs	

HBV Serology

All subjects will be tested locally for HBsAg, Anti-HBs, and Anti-HBc at Screening. Additionally, subjects ongoing in the Treatment Phase who are within 6 months of starting study treatment when Protocol Amendment 4 is implemented will be required to have HBV serology performed locally upon signing the updated ICF. Hepatitis B Virus serology is not required at Screening or for subjects ongoing in the Treatment Phase who are within 6 months of starting study treatment if this was performed as part of standard of care within 3 months prior to first dose.

HBV DNA Tests

Subjects who are positive for Anti-HBc or Anti-HBs will undergo testing for HBV DNA by PCR. Subjects with serologic findings suggestive of HBV vaccination (Anti-HBs positivity as the only serologic marker) and a known history of prior HBV vaccination do not need to be tested for HBV DNA by PCR. During and following study treatment, subjects who have history of HBV infection will be closely monitored for clinical and laboratory signs of reactivation of HBV as specified in the [Time and Events Schedule](#). Where required by local law, the results of HBV testing may be reported to the local health authorities.

- Hepatitis C Screening (local laboratory)
 - Hepatitis C antibody

If Hepatitis C antibody is positive, RNA PCR needs to be performed and confirmed negative prior to first study agent administration.

Daratumumab Interference Indirect Antiglobulin Testing (IAT) results

Blood group, Rh type, and IAT should be done before the first dose of daratumumab. Subject RBC phenotyping (standard or extended) is an alternative option to the IAT test, if locally required. Either method must be completed prior to first daratumumab infusion.

Daratumumab interferes with the indirect antiglobulin test (IAT), which is a routine pre-transfusion test performed to identify a patient's antibodies to minor antigens so that suitable donor blood can be given for transfusion. Daratumumab does not interfere with ABO/ Rhesus factor–D antigen (RhD) grouping/typing.

CD38 is expressed at very low levels on erythrocytes. Preliminary data indicate that daratumumab binds to the CD38 on erythrocytes, which results in a positive IAT (also known as indirect Coombs test) and will make complete blood typing difficult while subjects are receiving treatment. This effect occurs during daratumumab treatment and for up to 6 months after treatment ends. Despite daratumumab binding to CD38 on erythrocytes, no indication of clinically significant hemolysis was observed. Eleven of 78 subjects in Study GEN501 had blood transfusions during treatment with daratumumab.¹⁶ The preliminary data indicate that transfusion of these subjects treated with daratumumab was not adversely affected. In alternate situations, blood banks can eliminate the daratumumab interference with IAT by treating reagent RBCs with dithiothreitol.¹¹

Subjects will receive a patient identification wallet card for the study that includes the blood profile (ABO, Rh, and IAT or phenotyping) determined before the first infusion of daratumumab along with information on the IAT interference for healthcare providers/blood banks. Subjects are to carry this card throughout the treatment period and for at least 6 months after treatment ends.

Possible methods for blood banks to provide safe RBCs for transfusion to subjects receiving daratumumab include:

1. Providing ABO/RhD compatible, phenotypically (standard or extended phenotyping) or genotypically matched units
2. Providing ABO/RhD compatible, K-negative units after ruling out or identifying alloantibodies using DTT-treated reagent RBCs.

Uncrossmatched, ABO/RhD compatible RBC units should be administered if transfusion is needed emergently as per local blood bank practice. For additional details, refer to the daratumumab IB.

β2-microglobulin

Baseline β2-microglobulin will be measured in serum to assess lymphoma tumor burden as well as disease prognosis.

Pulmonary Function Test

Subjects with known or suspected COPD must have a FEV1 test during screening. Refer to Section 5.3 (Guidelines for Prevention of Infusion Reactions) for details on subjects with higher risk of respiratory complications.

Electrocardiogram (ECG)

Electrocardiogram (ECGs) will be performed as specified in the [T&E Schedule](#). During the collection of ECGs, subjects should be in a quiet setting without distractions (eg, television, cell phones). Subjects should rest in a supine position for at least 5 minutes before ECG collection and should refrain from talking or moving arms or legs. If blood sampling or vital sign measurement is scheduled for the same time point as ECG recording, then the procedures should be performed in the following order: ECG(s), vital signs, blood draw.

Vital Signs

Vital signs (pulse, temperature, and blood pressure) will be performed as specified in [T&E Schedule](#). It is recommended that blood pressure (sitting) and pulse measurements be preceded by at least 5 minutes of rest in a quiet setting without distractions (eg, television, cell phones). All measurements will be recorded in the source documents. Blood pressure and pulse/heart rate measurements will be assessed with a completely automated device. Manual techniques will be used only if an automated device is not available.

Physical Examination and ECOG Performance Status

A complete physical examination (including neurological examination) should be performed during the Screening Phase. Thereafter, only a symptom and disease directed physical examination is required. Height will be measured at screening only; weight will be measured regularly as specified in the [T&E Schedule](#). Abnormalities will be recorded in the appropriate sections of the eCRF. Eastern Cooperative Oncology Group (ECOG) Performance Status (refer [Attachment 1](#)) will be used to evaluate the impact of the disease status on the activities of daily

living. When scheduled, ECOG assessments should be obtained prior to dosing of daratumumab on Day 1 of each cycle.

8.7. Sample Collection and Handling

The actual dates and times of sample collection must be recorded in the eCRF or laboratory requisition form. If blood samples are collected via an indwelling cannula, an appropriate amount (1 mL) of serosanguineous fluid slightly greater than the dead space volume of the lock will be removed from the cannula and discarded before each blood sample is taken. After blood sample collection, the cannula will be flushed with 0.9% sodium chloride, United States Pharmacopeia (or equivalent)/sodium heparin of 10 U/mL and charged with a volume equal to the dead space volume of the lock. If a mandarin (obturator) is used, blood loss due to discard is not expected.

Refer to the [T&E Schedule](#) for the timing and frequency of all sample collections. Instructions for the collection, handling, storage, and shipment of samples are found in the laboratory manual that will be provided. Collection, handling, storage, and shipment of samples must be under the specified, and where applicable, controlled temperature conditions as indicated in the laboratory manual.

9. SUBJECT COMPLETION/WITHDRAWAL FROM THE STUDY

9.1. Completion

A subject will be considered to have completed the study if he or she has completed all protocol-specified procedures before the end of the study, has died before the end of the study, has not been lost to follow up, has not withdrawn consent for study participation before the end of the study, or has transitioned to commercial drug product.

9.2. Discontinuation of Study Treatment/Withdrawal From the Study

Discontinuation of Study Treatment

If a subject's study treatment must be discontinued, it will not result in automatic withdrawal of the subject from the study. The EoT Visits and Follow-up visit assessments should continue as specified in the [T&E Schedule](#).

A subject's study treatment (daratumumab) should be discontinued if:

- The investigator believes that for safety reasons or tolerability reasons (eg, AE) it is in the best interest of the subject to discontinue study treatment
- The subject becomes pregnant
- The subject withdraws consent for administration of study drug
- The subject initiates treatment with a prohibited medication
- The subject received concurrent (non-protocol) treatment for NKTCL
- The subject experiences unacceptable toxicity, including IRRs described in [Section 5.3](#)

- The subject's dose of daratumumab is held for more than 4 weeks in Cycles 1-6 or for more than 6 weeks in Cycle 7 and beyond (unless sponsor approves continuation)
- The subject experiences PD (see below and [Attachment 6](#)). Relapse from CR is not considered as disease progression.
- Daratumumab becomes commercially available (or when daratumumab can be accessed from another source) for this disease. At this time, the subject will be transitioned from study drug to commercial product and will be withdrawn from the study. In these circumstances, the sponsor and investigator will support transition of the subject to ensure that treatment continues and remains uninterrupted.
- A subject who experiences a second primary malignancy that cannot be treated by surgery or radiotherapy alone must be withdrawn from the study. However, a subject who develops a malignancy that can be cured surgically or with definitive radiotherapy may continue to receive the assigned study treatment and should continue to be followed for subsequent progression of NKTCL.

Subjects should be discontinued from study treatment if they have objective radiological PD based on real time BICR according to LUGANO Classification. Following centrally confirmed radiological PD subjects will be discontinued from study treatment and enter the Follow-up phase.

For subjects who have PD as evidenced by unambiguous clinical information (eg. pathologically demonstrated as PD), before such subjects discontinue study treatment due to PD, sites will document PD by completing and faxing a PD form to the sponsor as soon as possible and within 48 hours of PD assessment; EoT steps will be performed. The study responsible physician will confirm that treatment should be discontinued. After confirmation from the sponsor, study treatment may be discontinued and the subject can enter into Follow-up phase. If a subject discontinues study treatment for any reason other than PD, then disease assessments should be obtained as specified in the [T&E Schedule](#).

Withdrawal From the Study

A subject will be withdrawn from the study for any of the following reasons:

- Lost to follow-up
- Withdrawal of consent
- Death
- Sponsor terminates the study.

If a subject is considered lost to follow-up, every reasonable effort must be made by the study-site personnel to contact the subject and determine the reason for discontinuation/withdrawal. The measures taken to follow up must be documented.

When a subject withdraws before completing the study, the reason for withdrawal is to be documented in the eCRF and in the source document (refer Section [8.1.4](#) and Section [15.2.3](#) for details on collection of long-term survival status). Study drug assigned to the withdrawn subject

may not be assigned to another subject. Subjects who withdraw will not be replaced. If a subject withdraws from the study before the EoT, assessments should be obtained.

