8.1.3. Treatment Phase

The Treatment Phase will begin at first intake of study drug and will continue until study drug discontinuation due to PD, consent withdrawal or unacceptable toxicity. Details of the procedures performed during the Treatment Phase are outlined in the [T&E Schedule](#). A window of ± 3 days is allowed for visits to the clinic. The start of each cycle should be scheduled relative to Cycle 1 Day 1 and should not change if within-cycle visits (eg Cycle 1 Day 15; Cycle 2 Day 22) have shifted within the allowed window.

Subjects will be closely monitored for AEs, laboratory abnormalities, and clinical response. Clinical evaluations and laboratory studies may be repeated more frequently, if clinically indicated. If PD is diagnosed, then the subject will discontinue study treatment, complete the EoT Visit, and enter the Follow-up Phase.

End-of-Treatment

Unless a subject withdraws consent for study participation or is lost to follow up, an EoT Visit is to occur within 30 days (+7 days' window) after the last dose of all study treatments. Every effort should be made to conduct the EoT Visit before the subject starts subsequent treatment eg, anticancer therapy. If a subject is unable to return to the site for the EoT Visit, then the subject should be contacted to collect information on AEs and concomitant medications that occur up to 30 days after the last dose of study treatment.

Subjects will be discontinued from study treatment if they have objective radiological PD based on real time BICR according to LUGANO Classification.¹² Following centrally confirmed radiological PD, site will document the PD by completing and faxing a PD form to the sponsor and the study responsible physician will provide written confirmation based on the central confirmed radiological PD that study treatment may be discontinued and recorded in interactive web response system (IWRS) before the subject can enter the Follow-up Phase.

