8.2. Efficacy Evaluations

Disease evaluations will be performed at Screening, every 8 weeks (± 7 days) for the first 6 months and thereafter, every 16 weeks (± 7 days) until PD, withdrawal of consent from study participation, or the end of study.

Radiological and PET-CT scans should be performed and collected according to instructions from the independent imaging laboratory. A BICR will be performed to review all the imaging data and clinical information per pre-defined independent central review charter.

The central reviewers will assess disease status based on the Revised Criteria for Response Assessment: LUGANO classification, provided in [Attachment 6](#).¹² Similar methodology should be used for disease assessment at screening and throughout the course of the study. The treatment discontinuation due to PD should be based upon the real time reading results conducted by the central readers. On the basis of clinical information, if PD is confirmed, then for all such subjects, as soon as PD is confirmed by local assessment, the sponsor should be informed immediately.

In order to maximally reduce potential bias between different readers, rigorous methodology will be employed and thus, ensure robustness of the primary endpoint assessment of ORR which is based on BICR. All radiological scans and collected clinical information will be sent to a sponsor appointed Clinical Research Organization (CRO) for a real time BICR. All treatment decisions will be based on such timely central review result. Subjects who are determined to have progressed according to LUGANO classification by the investigator will have scans centrally reviewed for confirmation of objective disease progression. If PD is not confirmed after central review, daratumumab treatment should be continued until centrally documented PD. This procedure may not be followed if the clinical information of subject (eg, Pathologically demonstrated PD) is sufficient enough to demonstrate PD, for such cases, PD confirmation from sponsor study physician is also required.

Definition of Measurable Disease, Assessable Disease, Target Lesion, and Non-Target Lesion

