Response and Site	PET-CT–Based Response	CT-Based Response
Nonmeasured lesions	Not applicable	No increase consistent with progression
Organ enlargement	Not applicable	No increase consistent with progression
New lesions	None	None
Bone marrow	No change from baseline	Not applicable
Progressive disease	Progressive metabolic response	Progressive disease requires at least 1 of the following
Target nodes/nodal masses, extranodal lesions	Score 4 or 5 with an increase in intensity of uptake from virtually determined nadir	PPD progression: An individual target (nodal or extranodal) must be abnormal with: Node >1.5 cm in LDi or extranodal lesion >1.0 cm in any axis; Increase by $\geq 50\%$ from PPD nadir and An increase in LDi or SDi from nadir: ≥ 0.5 cm for lesions ≤ 2 cm ≥ 1.0 cm for lesions > 2 cm In the setting of splenomegaly, the splenic length must increase by $> 50\%$ of the extent of its prior increase beyond baseline (eg, a 15-cm spleen must increase to > 16 cm). If no prior splenomegaly, must increase by at least 2 cm from baseline New or recurrent splenomegaly
Nonmeasured lesions	None	New or clear progression of preexisting nonmeasured lesions
New lesions	New FDG-avid foci consistent with lymphoma rather than another etiology (eg, infection, inflammation). If uncertain regarding etiology of new lesions, biopsy or interval scan may be considered.	Regrowth of previously resolved lesions A new node > 1.5 cm in LDi; A new extranodal site > 1.0 cm in any axis; if < 1.0 cm in any axis, its presence must be unequivocal and must be attributable to lymphoma; Assessable disease of any size unequivocally attributable to lymphoma
Bone marrow	New or recurrent FDG-avid foci	New or recurrent involvement

Response and Site	PET-CT–Based Response	CT-Based Response

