5.3.1. Definition

Complete response (CR) rate is defined as the proportion of subjects who achieve CR based on BICR and will be analyzed similarly as the primary endpoint ORR.

Progression-free survival (PFS) is defined as the duration from the date of the first daratumumab dose to the date of progression/relapse based on BICR or death, whichever comes first. For those subjects who are still alive without progression/relapse, PFS will be censored at the last adequate tumor assessment. Subjects who are progression-free and alive or have unknown status will be censored at last tumor assessment. Subjects with no post baseline disease assessment will be censored on Day 1. Subjects who started a subsequent anti-cancer therapy in the absence of progression will be censored at the last disease assessment before the start of subsequent therapy. Subjects whose diseases have not progressed and who are still alive at the end of the study or clinical cutoff will be censored at the last adequate disease assessment.

Duration of response (DoR) will be duration from the date of the initial documentation of a response to the date of first documented evidence of progressive disease based on BICR (PD; or relapse for subjects who experience CR) or death and calculated only for responders. For those subjects who are still without progression/relapse, DoR will be censored at the last adequate tumor assessment.

Time to response (TTR) is defined as the duration from the date of the first dose of daratumumab to the earliest date that a response (CR/PR based on BICR) is first documented. Descriptive analysis will be performed for responders including median, mean, standard deviation, and range.

Overall survival (OS) is defined as the duration from the date of the first daratumumab dose to the date of death. Subjects who withdraw consent from the study or are lost to follow-up will be censored at the time of withdrawal or lost to follow-up. For those subjects who are still alive at the time of analysis, OS will be censored at the last date known to be alive.

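### Protocol 9.2 says relapse from CR is not progression, while Attachment 6 and the BICR stopping rule class returning disease as progression and stop treatment

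*Protocol*

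**What the plan says.** Protocol Section 9.2 lists the reasons for stopping daratumumab. Its bullet on PD points to the text further down and to Attachment 6, and then adds: "Relapse from CR is not considered as disease progression". The text further down in the same section reads: "Subjects should be discontinued from study treatment if they have objective radiological PD based on real time BICR according to LUGANO Classification".

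Section 8.1.3 gives the same rule: "Subjects will be discontinued from study treatment if they have objective radiological PD based on real time BICR according to LUGANO Classification". Sections 8.2 and 8.2.6 also tie discontinuation for PD to the real-time central read, and 8.2 states the converse: "If PD is not confirmed after central review, daratumumab treatment should be continued until centrally documented PD". None of these places excepts a subject with a prior CR. The departures they allow concern how PD is evidenced (unambiguous clinical information such as pathology, or PD by local evaluation only).

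Attachment 6 has four categories: complete response, partial response, no response or stable disease, and progressive disease. Under progressive disease it lists:

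- new lesions, CT column: "Regrowth of previously resolved lesions";
- new lesions, PET column: new FDG-avid foci attributed to lymphoma;
- bone marrow, PET column: "New or recurrent FDG-avid foci";
- bone marrow, CT column: "New or recurrent involvement".

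The endpoint definitions (Protocol 10.3.2, SAP 5.3.1) name relapse. PFS ends at progression or relapse by BICR, or at death. DoR ends at the first documented PD by BICR, which the SAP glosses as "PD; or relapse for subjects who experience CR) or death and calculated only for responders".

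Neither document defines relapse from CR.

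**The concern.** The sentence in 9.2 decides whether the PD stopping criterion applies to a subject in CR whose lymphoma returns. Read alone, it says the criterion is not met. Read through Attachment 6 and the BICR rule, the criterion is met and treatment stops.

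Other procedures hang on the same answer. Disease evaluations under 8.2 run until PD. The post-PD follow-up in 8.1.4 begins only once PD is centrally evidenced and confirmed by the study physician. Section 7.3 prohibits other NKTCL treatment on study, and 9.2 makes receiving it a reason to stop daratumumab, so the reading adopted also bears on when another therapy could begin. This concerns the handling of patients with returning lymphoma, and exposure and disposition summaries would partly reflect which sentence was followed.

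**Working it through.** There is no stated figure to reproduce; the check is a comparison of texts.

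**1. Test case.** A subject has a CR by BICR. A later central read shows regrowth of a resolved lesion on CT, a new FDG-avid lymphoma focus, or recurrent marrow disease.

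**2. Classification.** Under Attachment 6 each finding is progressive disease. No other category fits: complete response, partial response and stable disease all require no new lesions, CT-based stable disease also requires that no PD criterion is met, and there is no relapse row.

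**3. Instruction that follows.**

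| Source | Is the read PD? | Instruction |
|---|---|---|
| Attachment 6 with 8.1.3 | Yes | Discontinue |
| 8.2 and 8.2.6 | Yes, by the central read | Discontinuation rests on that read |
| 9.2, closing text | Yes, by Lugano | Discontinue |
| 9.2, PD bullet, last sentence | No | PD criterion not met |

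The last two rows are in the same section, and the bullet in the last row itself cites Attachment 6.

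**4. Where there is no conflict.** A node just above 1.5 cm in longest diameter no longer meets the CT criterion for CR. If its increase from nadir is below 50%, it does not meet the PD size criterion either. Unless the central reader calls it regrowth of a resolved lesion, neither text makes it PD. The contradiction is therefore confined to returning disease that meets an Attachment 6 PD criterion.

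**5. PFS and DoR.** Both definitions name relapse, so the event is dated at the BICR relapse whether or not 9.2 calls it progression. The DoR wording puts relapse inside documented PD, which disagrees with 9.2 on terminology but leaves the date clear.

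**6. Response endpoints.** ORR and CR rate count subjects who achieve response, so a later relapse removes nobody. The futility boundary (at most 1 of 15) and the rejection boundary (8 or more of 32) are counts of such responders.

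**7. Size.** The number affected is N × P(CR) × P(relapse on study, given CR) × P(relapse meets an Attachment 6 PD criterion). The documents give N: 32, or about 32 + 35 = 67 with the optional expansion. They give none of the three probabilities, so no count follows; the number of CR subjects is only a ceiling. For one affected subject, the next scheduled evaluation after the disputed read falls 8 weeks later in the first 6 months and 16 weeks later thereafter.

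**The case against.** **Central control.** Sites do not decide alone. Section 8.2 bases treatment decisions on the central read, and 8.1.3 requires a PD form and written confirmation from the study responsible physician. One sentence stands against a rule stated in four places. This stands in part: it makes divergent handling less likely. It does not remove the conflict, because the physician who confirms works from the same protocol, and the sentence sits in the section that lists the stopping reasons.

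**A deliberate carve-out.** Relapse might mean a loss of CR that stays below the PD thresholds, in which case nothing conflicts (step 4). The documents do not say so. Inclusion criterion 3.1 uses relapse for failure after remission, without any such threshold. If the narrow sense was intended, its definition is missing.

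**The BICR charter.** It may deal with relapse. It was not available, so the point is limited to the protocol text.

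**Stronger readings that a reader might infer.**

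- *PFS and DoR are contradictory or biased.* Not supported: a stopping rule and an endpoint event may differ, and both definitions name relapse. The SAP rule that censors PFS at subsequent therapy mentions only the absence of progression, but under the main definition a relapse before that therapy is already the event.
- *OS depends on which sentence is followed.* Not supported: OS runs from first dose to death whatever the treatment status, and nothing in the documents links it to this choice.
- *A given number of subjects is affected.* Multiplying an assumed CR rate by N counts all CR subjects, not those who relapse.

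**Conclusion.** Wrong as written, and it should be corrected. For a CR subject whose returning disease meets an Attachment 6 PD criterion, the protocol gives opposite instructions on stopping treatment, and hence on the scan schedule and entry to post-PD follow-up. This rests on relapse having its ordinary meaning, since no other is given, and on the protocol text without the charter. The number of subjects cannot be derived and may be small. The primary analysis is not at risk; the reason to act is that the contradiction governs treatment of individual patients.

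**What to change.** Reconcile the sentence in 9.2 with 8.1.3, 8.2, 8.2.6 and Attachment 6, so that a BICR read of returning disease after CR has one stated meaning for discontinuation, scans and follow-up. If relapse from CR is meant as something other than Attachment 6 PD, such as loss of CR below the PD thresholds, define it and align the central read with that definition. Using the same term in the DoR definition would remove the remaining inconsistency of wording. Which clinical rule applies is for the sponsor to decide.

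Cost: one clarified sentence in the next amendment if the texts are simply aligned. A separate relapse category costs more, because Attachment 6 and the central read would also have to change. Neither route alters the sample size or the response analysis.
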